4.2. Inclusion Criteria

Before enrollment in the study, subjects must fulfil all of the following criteria:

- 1. Subject (or legally authorized representative) is willing and able to provide informed consent and comply with all protocol requirements.
- Agrees to the collection of nasopharyngeal swabs and venous blood and all other protocol-specified procedures.
- 3. Male or non-pregnant female adult ≥18 years of age at time of enrollment.
- 4. Hospitalized and has laboratory-confirmed infection with SARS-CoV-2.
- 5. Symptom onset was ≤14 days prior to Screening
- 6. Has SpO₂ <94% on room air
- 7. Has at least one of respiratory rate >24 breaths/minute or cough
- 8. Lung involvement as confirmed by radiographic infiltrates observed on imaging (chest X-ray, CT scan, or an equivalent test)

- 9. Women of childbearing potential (as defined in (CTFG 2014)) must have a negative pregnancy test at screening and agree to abstinence or the use at least one of the following highly effective forms of contraception (with a failure rate of <1% per year when used consistently and correctly). Contraception or abstinence must be continued for the duration of the study following discharge from the hospital, and for up to 50 days after the last dose of study drug:
 - combined (estrogen and progestogen containing) hormonal contraception associated with inhibition of ovulation:
 - oral
 - intravaginal
 - transdermal
 - progestogen-only hormonal contraception associated with inhibition of ovulation:
 - oral
 - injectable
 - implantable
 - intrauterine device
 - intrauterine hormone-releasing system
 - vasectomized partner with confirmed azoospermia

All females will be considered of childbearing potential unless they are postmenopausal (at least 12 months consecutive amenorrhea in the appropriate age group without other known or suspected cause) or have been sterilized surgically (eg, bilateral tubal ligation, hysterectomy, bilateral oophorectomy).

10. Men sexually active with women of childbearing potential who have not had a vasectomy must agree to use a barrier method of birth control during the study following discharge from the hospital and for up to 50 days after the last dose of study drug.

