7. STUDY ASSESSMENT AND PROCEDURES

7.1. Schedule of Events and Study Parameters

Table 3: Schedule of Events

Assessment/Activity	Screening	Day		Treatm	ent Peri	iod		Follow-up		Notes
		1	Days 2-6	Day 7	Days 8-13	Day 14/ EOT	Days 15-27	Day 28/ EOS	Day 60 ±3	Screening and Day 1 should occur within a 1-day period; where they occur on the same day, assessments need not be repeated. Subjects remaining in hospital will undergo the assessments specified. All subjects will undergo the assessments specified for Day 14, Day 28, and Day 60 even if they are discharged from the hospital prior to Day 28.
Informed consent	X									
Medical history	X									
WHO ordinal scale assessment	X									(WHO 2020)
Pregnancy test	X							Х	X	WOCBP only. Pregnancy test can be serum βHCG or urine. The Day 60 test should be taken at home and self-reported during telephone contact.
Vital signs	X	X	X	Х	X	X	X	Х		Vital signs will include oxygen saturation daily for primary endpoint assessment in addition, temperature, respiratory rate, and blood pressure will also be assessed.
Cough and dyspnea assessments	Х	Х	X	Х	Х	Х	X	Х		Cough and dyspnea are assessed daily on a patient reported scale of severe, moderate, mild, or absent.
Body weight and height	X									
Physical examination	X	X	X	X	X	X		X		Full physical examination (including a minimum of general appearance, head, eyes, ears, nose, mouth, throat, heart, thyroid, chest and lungs, abdomen, extremities, neuromuscular system, skin, and lymph nodes) will be completed during screening; at all other timepoints the examination will be targeted.

Assessment/Activity	Screening	Day						Follow-up		Notes
		1 -	Days 2-6	Day 7	Days 8-13	Day 14/ EOT	Days 15-27	Day 28/ EOS	Day 60 ±3	Screening and Day 1 should occur within a 1-day period; where they occur on the same day, assessments need not be repeated. Subjects remaining in hospital will undergo the assessments specified. All subjects will undergo the assessments specified for Day 14, Day 28, and Day 60 even if they are discharged from the hospital prior to Day 28.
Chest X-ray	X					X				X-ray taken within 24 hours prior to Screening will be accepted. CT scan will be accepted in place of the X-ray if taken with 48 hours prior to Screening.
Nasopharyngeal swab		X	X	X		X		X		Nasopharyngeal swab will be taken on Days 1, 2, 4, 7, 14, and 28.
Hematology, coagulation, and clinical chemistry assessment	Х	Х	Х	Х	Х	Х		Х		Assessments taken within 24 hours prior to Screening will be accepted.

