8.4.5. Baseline Descriptive Statistics

Demographic and baseline characteristics of subjects (including ordinal scale score (WHO 2020) will be summarized descriptively by means and standard deviations for continuous variables, and frequency distribution for categorical variables. Summaries will be performed based on all randomized subjects.

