### 3. STUDY DESIGN

#### 3.1. Overall Design

This is a randomized, double-blind, placebo-controlled, multicenter, Phase 2/3, 28-day study with safety follow-up by telephone call at Day 60. The study is designed to evaluate the efficacy and safety of PTC299 as compared with placebo in hospitalized adult subjects with confirmed pneumonia, diagnosed with COVID-19, and not requiring mechanical ventilation. All subjects regardless of receiving PTC299 or placebo, will also receive standard of care as defined per local written policies or guidelines. Eligible subjects will be equally (1:1) randomized to one of the two following treatment arms:

Arm A - Subjects in arm A will receive PTC299 200mg twice a day (BID) (morning and evening at approximately 12-hour intervals) on Days 1 to 7 followed by 50 mg QD (in the morning) on Days 8 to 14. Subjects will be followed up to Day 28 with a safety follow-up phone call at Day 60.

Arm B - Subjects in arm B will receive the matching placebo BID (morning and evening at approximately 12-hour intervals) on Days 1 to 7 followed by the matching placebo QD (in the morning) on Days 8 to 14. Subjects will be followed up to Day 28 with a safety follow-up phone call at Day 60.

Randomization will be stratified by the following three stratification factors:

- Age ( $\leq 62$  vs  $> 62$ )
- Remdesivir use (yes vs no)
- Dexamethasone use (yes vs no)

The study is expected to enroll approximately 380 subjects with two planned interim analyses. The first interim analysis is planned when approximately 40 randomized subjects (20 in each arm) have been enrolled and followed to Day 28 or discontinued due to death, or withdrawal consent, or lost-to-follow-up to assess the safety of the study drug. The 2nd interim analysis is planned when approximately 163 events have been observed (approximately 190 subjects have been followed up to 28 days) to assess the futility of the study.

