##### **4.5.2. Baseline Characteristics**

The following baseline characteristics will be summarized by treatment arms and overall.

Stratification factors:

- Age ( $\leq 62$  vs  $>62$ )
- Dexamethasone use (yes vs no)
- Remdesivir use (yes vs no)

Baseline disease risk factors:

- Chronic kidney disease (yes vs no)
- COPD/asthma (yes vs no)
- Immunocompromised (yes vs no)
- Type 2 diabetes (yes vs no)
- Heart disease (yes vs no)
- Sickle cell disease (yes vs no)
- Obesity (yes vs no)
- Hypertension (yes vs no)

Baseline disease characteristics:

- WHO ordinal scale for clinical improvement
- Received any of COVID-19 treatment as SOC (yes vs no)
- Time from symptom onset to randomization
- Time from COVID-19 diagnosis to randomization
- COVID-19 initial symptoms

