##### 4.9.1. Primary Efficacy Analysis

The primary endpoint is the time from randomization to respiratory improvement (T2RI), defined as  $\text{SpO}_2 \geq 94\%$  on room air sustained until discharge from the hospital or the end of the study (Day 28).

All hospitalized subjects will be followed fully to Day 28 with efficacy measurements taken daily unless they die, are lost to follow-up, or withdraw consent. For subjects who are discharged from the hospital prior to Day 28 without achieving respiratory improvement,  $\text{SpO}_2$  measurements will be taken daily until Day 28. All measurements recorded will be used for efficacy analysis.

Subjects who achieved  $\text{SpO}_2 \geq 94\%$  and sustained to Day 28 or discharge without taking any COVID-19 rescue therapy during the study will be considered as achieving respiratory improvement event and the event date will be the first date of achieving  $\text{SpO}_2 \geq 94\%$ . For all other subjects i.e., a). randomized but had no follow-up; b). initiated any COVID-19 rescue therapy during the study, where a rescue therapy is defined as any additional medication, exclusive of SOC, used to treat worsening of COVID-19 symptoms and recorded as rescue therapy on the eCRF; c). lost follow-up prior to Day 28 d). died prior to Day 28; e). withdrawn consent prior to Day 28; f). had full follow-up without achieving sustained  $\text{SpO}_2 \geq 94\%$ , will be censored at Day 28.

Kaplan-Meier (KM) plots of time to respiratory improvement will be presented. Median time to respiratory improvement will be estimated via the Kaplan-Meier product limit method.

A two-sided 95% confidence interval (CI) for the median time to respiratory improvement will be computed for PTC299 and placebo cohorts based on a log-log transformed CI for the survivor function  $S(t)$ . Time to respiratory improvement will be compared between treatment groups using stratified log-rank test by randomization strata.

Hazard ratio and corresponding two-sided 95% CIs will be estimated using a Cox proportional hazards model, with treatment arm as a single covariate, stratified by the stratification factors.

Respiratory improvement rates at Days 7, 14, and 28 will also be estimated using KM estimates on the time to respiratory improvement curve. Associated two-sided 95% CIs for each treatment group and the difference between the 2 treatment groups will be calculated using Greenwood's formula for variance derivation.

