#### **4.9.1.1. Sensitivity Analysis for Primary Endpoint**

Three sensitivity analyses will be performed for the primary endpoint as follows:

- Randomized subjects without any follow-up will be censored at the randomization date.
- Subjects will not be censored by rescue therapy in the primary analysis.
- An additional variable of time from symptom onset to randomization ( $\leq 7$  days versus  $>7$  days) will be added in the primary analysis model.

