###### **The proportion of subjects requiring supplemental oxygen or non-invasive ventilation at any point during the study in subjects who did not require supplemental oxygen at baseline**

Number and the percentage of subjects requiring supplemental oxygen or noninvasive ventilation during the study in subjects who did not require supplemental oxygen at baseline will be summarized by treatment groups. Cochran Mantel-Haenszel test will be used to compare the treatment difference.

A by-subject listing will also be provided for subjects requiring supplemental oxygen or non-invasive ventilation.

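### No baseline respiratory severity measure enters the primary, sensitivity or subgroup analyses, although WHO score and SpO2 are collected: a cheap improvement, not an error

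*SAP*

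**What the plan says.** The endpoint is time until SpO2 on room air reaches 94% and stays there to discharge or Day 28. SAP 4.9.1 tests it with a log-rank test stratified by the randomization strata and estimates the HR from a "Cox proportional hazards model, with treatment arm as a single covariate, stratified by the stratification factors". Protocol 8.4.2 agrees. The strata are age (62 or under against over 62), remdesivir use and dexamethasone use (SAP 3.1 and 3.5).

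SAP 4.9.1.1 has three sensitivity analyses. One changes the censoring of subjects without follow-up, one drops censoring at rescue therapy, and one brings in "An additional variable of time from symptom onset to randomization". SAP 4.11 lists twelve subgroups: the three stratification factors, eight comorbidities, and symptom duration of 5 days or less.

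The severity data exist. The schedule in protocol 7.1 places the WHO ordinal assessment at Screening, and vital signs at Screening and daily: "Vital signs will include oxygen saturation daily for primary endpoint assessment". Their stated baseline use is descriptive. Protocol 8.4.5 reads "Demographic and baseline characteristics of subjects (including ordinal scale score (WHO 2020) will be summarized descriptively", and SAP 4.5.2 lists "WHO ordinal scale for clinical improvement" among the baseline disease characteristics tabulated by arm.

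**The concern.** Respiratory status at entry is the obvious candidate predictor of how soon SpO2 recovers. Entry requires "Has SpO₂ <94% on room air" with no lower limit, and the plan recognizes that oxygen need differs at entry: one secondary endpoint is analyzed "in subjects who did not require supplemental oxygen at baseline will be summarized by treatment groups". Yet WHO score, baseline SpO2, respiratory rate and oxygen support are all absent from the strata, the primary test and model, the sensitivity models and the subgroups.

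If severity predicts the endpoint beyond the three strata, a chance difference between arms moves the observed HR in one direction or the other. The baseline table would show a WHO imbalance, but any severity-adjusted HR produced in response would be post hoc. The plan already adds symptom duration to the primary model for a similar purpose, so a severity model would be the same kind of addition.

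**Working it through.** **1. The plan's own power.** Inputs from SAP 3.6: 326 events, HR 1.38, two-sided alpha 0.05, medians 11 and 8 days (11/8 = 1.375), 380 subjects 1:1, 28 days of follow-up. Schoenfeld: power = Φ(ln HR × √events / 2 − 1.96), with √326 / 2 = 9.028.
- HR 1.38: 0.3221 × 9.028 − 1.96 = 0.948, power 82.8%.
- HR 1.375: 0.3185 × 9.028 − 1.96 = 0.915, power 82.0%.
- Day 28 rates: 1 − 2^(−28/11) = 0.829 and 1 − 2^(−28/8) = 0.912, so 190 × (0.829 + 0.912) ≈ 331 events.
- If the non-binding 1.091 futility boundary is always obeyed, power is 80.0 to 80.9%.

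The stated power of more than 80% therefore holds without adjustment.

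**2. Power if the adjusted model were primary.** The documents give no prognostic strength, so these inputs are assumptions: improvement hazard falling by a factor of 1.2, 1.35 or 1.5 per SD of severity; a three-level score split 30/50/20%; WHO category and SpO2 each correlated 0.5 or 0.7 with severity; strata unrelated to severity, dexamethasone tracking it, or all three tracking it. The unadjusted HR was held at 1.375, with 380 subjects, eight strata, exponential times and a Day 28 cut-off. There were 18 settings of 10,000 simulated trials; the SE of the paired gain is 0.15 to 0.28 points. The planned stratified log-rank test has 80 to 82% power. Gains in percentage points:

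| Severity HR per SD | WHO category + SpO2 | WHO category alone |
|---|---|---|
| 1.2 | +0.1 to +0.7 | 0.0 to +0.5 |
| 1.35 | +0.9 to +2.3 | +0.4 to +1.4 |
| 1.5 | +1.5 to +4.1 | +0.6 to +2.2 |

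If severity is not prognostic, 0.1 to 0.2 points are lost. One-sided type I error is 2.1 to 2.7% planned and 2.0 to 2.6% adjusted. A separately programmed simulation of four of these settings (4,000 trials each) gave +0.5 to +4.0 with both measures and +0.5 to +2.0 with WHO category alone.

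**3. How far the range depends on the assumptions.**
- Severity measured exactly, HR 1.5 per SD: +6.1.
- Severity binary, present in half the sample, halving the improvement rate (ln 2 × 0.5 = 0.347, or HR 1.41 per SD), measured exactly, unadjusted HR held near 1.38: +5.6, or +4.3 if it tracks dexamethasone.
- The same with a threefold slower rate (HR 0.33) and the conditional HR held at 1.38: 67.8% to 81.4%, or +13.6.
- A fraction of never-improvers that depends on severity (8% at mean severity): planned power 77 to 78%, gain +3.6 to +6.4 with both measures and +2.6 to +4.2 with WHO category alone. This setting makes severity more prognostic.

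**4. Chance imbalance.** The arm difference in mean severity has SD √(2/190) = 0.10. It exceeds 0.2 SD in either direction in 3 to 5% of simulated trials (normal approximation without stratification: 5%). At 0.2 SD and HR 1.35 per SD, the first-order shift in log HR is 0.2 × ln 1.35 = 0.060. An HR of 1.375 then becomes about 1.30 if the PTC299 arm is sicker and about 1.46 if the placebo arm is. The simulated averages are 1.30 to 1.31 and 1.44 to 1.46. Adjusting for both measures gives 1.33 to 1.36 and 1.41 to 1.44. Adjustment removes 32 to 62% of the shift with both measures and 16 to 38% with WHO category alone. These trials are already averaged into the 80 to 82%.

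**5. What the adjusted HR estimates.** It is conditional on severity. Where the unadjusted HR is about 1.38, the adjusted one is about 1.38 to 1.41 even without imbalance. That difference of up to 0.03 is similar in size to the 0.02 to 0.05 changes in step 4.

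**The case against.** The plan is valid, the protocol and SAP agree, and the stated power reproduces, so what remains could be called preference. Entry criteria already narrow severity (SpO2 below 94%, radiographic infiltrates, no mechanical ventilation). Dexamethasone stratification may carry part of it, and the introduction to the protocol ties age to risk of death. The WHO table will reveal an imbalance, and a marked one is uncommon. Adjustment with WHO category alone removes well under half of the shift. All of this stands. It limits the benefit but does not remove the case for settling the adjusted model in advance.

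Three stronger readings are tempting and are not supported:
- A reader might infer that the trial is underpowered or its test biased without severity. Randomization protects the type I error, and 326 events give the stated power.
- A reader might infer that the small SAP addition buys up to 4 points. It buys none, because the log-rank test stays primary. The gain belongs to a different choice, its upper end needs a room-air SpO2 as well as the WHO score, and its size rests on assumptions that no section supplies.
- A reader might take the gap between adjusted and unadjusted HR as the effect of imbalance. It also contains the conditional-versus-marginal difference in step 5 and cannot be split by inspection.

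**Conclusion.** The omission is confirmed throughout both documents, and it is a modest missed opportunity, not an error. As a sensitivity analysis, the severity model adds no power. Its value is a prespecified severity-adjusted HR beside the primary one, should the arms differ by chance. As the primary model it would gain about 0 to 2 points with WHO category alone and 0 to 4 with WHO category plus SpO2, given severity HR at most 1.5 per SD and imperfect measurement. It would gain more if severity is more prognostic or better measured, and lose 0.1 to 0.2 points if severity is not prognostic. Confidence is high on what the plan omits and medium on the size. The point sits at the low end of what should be changed.

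**What to change.** Before database lock and unblinding:

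1. Add a fourth sensitivity analysis to SAP 4.9.1.1: a Cox model stratified by the randomization factors, with treatment and baseline WHO ordinal category as covariates.
2. Set one rule for sparse WHO levels, applied to pooled blinded data and used for both the model and the subgroup. For example, merge adjacent levels until each holds at least 10% of subjects (38 of 380), which matches the existing threshold in SAP 4.11. State how a missing score is handled, for example by assigning the most frequent pooled level in the model.
3. Add screening SpO2 as a continuous covariate only if a room-air value is confirmed to be recorded. Eligibility needs one, but the schedule does not say that the recorded value is on room air. Otherwise use WHO category alone.
4. Add the merged WHO category to the subgroups in SAP 4.11.
5. Keep the primary test, the primary HR and the 1.091 futility comparison unchanged. Report the adjusted HR beside the primary HR, noting that it is conditional on severity and that the gap between the two is not the imbalance effect alone.

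The cost is a short SAP addition, one data check and one extra model, with no protocol amendment.

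Option: the sponsor may make the adjusted model primary, with the unadjusted analysis as supporting. That requires amending the protocol synopsis, protocol 8.4.2 and SAP 4.9.1, and stating that the 1.091 comparison stays on the unadjusted stratified HR.

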#### **4.9.1.1. Sensitivity Analysis for Primary Endpoint**

Three sensitivity analyses will be performed for the primary endpoint as follows:

- Randomized subjects without any follow-up will be censored at the randomization date.
- Subjects will not be censored by rescue therapy in the primary analysis.
- An additional variable of time from symptom onset to randomization ( $\leq 7$  days versus  $>7$  days) will be added in the primary analysis model.

#### **4.9.2. Secondary Efficacy Analyses**

##### **4.9.2.1. Respiratory Functions**

###### **The proportion of subjects requiring invasive ventilation at any point during the study**

Number and the percentage of subjects requiring invasive ventilation during the study will be summarized by treatment groups. Cochran Mantel-Haenszel test will be used to compare the treatment difference.

A by-subject listing will also be provided for subjects requiring invasive ventilation.

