4.3. Exclusion Criteria

Subjects will not be permitted to enroll in the study if any of the following criteria apply:

- 1. Requires mechanical ventilation
- 2. Current participation in any other interventional study.
- 3. Alanine transaminase/aspartate transaminase levels (ALT/AST) ≥3times the upper limit of normal (×ULN) or total bilirubin (Tbili) ≥2×ULN.
- 4. Lymphocyte count <500 lymphocytes/μL or hemoglobin <11.0 g/dL
- 5. Stage 4 severe chronic kidney disease or requiring dialysis (ie, estimated glomerular filtration rate <30)
- 6. Any other condition, that in the opinion of the investigator, may be cause to exclude the subject from the study.

- 7. Use of steroids (except dexamethasone), sensitive CYP2D6 substrates, CYP2C inducers, IL-6 neutralizing antibodies, IL-6 receptor inhibitors, or any investigational therapy.
- 8. Pregnancy or breast feeding.
- 9. Anticipated transfer to another hospital which is not a study site within 72 hours.
- 10. Known allergy to PTC299 or excipients.

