#### **2.2.2. Secondary Endpoints**

- The proportion of subjects requiring invasive ventilation at any point during the study
- The proportion of subjects requiring supplemental oxygen or non-invasive ventilation at any point during the study in subjects who did not require supplemental oxygen at baseline
- Time from randomization to defervescence in subjects presenting with fever at enrollment (temperature of  $\geq 37.6^{\circ}\text{C}$  axilla,  $\geq 38.0^{\circ}\text{C}$  oral, or  $\geq 38.6^{\circ}\text{C}$  tympanic or rectal)
- Time from randomization to respiratory rate  $\leq 24$  breaths/minute on room air
- Time from randomization to cough reported as mild or absent (on a scale of severe, moderate, mild, absent, in those with cough at enrollment rated severe or moderate)
- Time from randomization to dyspnea reported as mild or absent (on a scale of severe, moderate, mild, absent, in those with dyspnea at enrollment rated as severe or moderate)

- Attenuation of immune responses as indicated by:
  - reduction in cytokine levels, potentially including interleukin (IL)-2, IL-6, IL-7, IL-17, G-CSF, IP-10, MCP-1, MIP1- $\alpha$ , and TNF- $\alpha$
  - reduction in levels of acute phase proteins, potentially including ferritin, C-reactive protein, D-dimer, and cardiac troponin
  - normalization in the complete blood count
  - changes in other laboratory parameters potentially including decreases in lactate dehydrogenase, prothrombin time, albumin
- Reduction in viral load
- Duration of hospitalization measured in days
- Mortality at Day 28
- Overall safety profile characterized by type, frequency, severity, timing, and relationship to study treatment of any adverse events (AEs) or laboratory abnormalities.

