### **4.2. Analysis Populations**

#### **4.2.1. Intent-to-Treat (ITT) Population**

ITT population will include all randomized subjects. The ITT population will be used in all efficacy analyses and subjects will be grouped based on the arm they are randomized to. If a subject receives treatment different from the one to which he/she was randomized, the subject's efficacy data will be analyzed "as randomized."

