#### 4.9. Efficacy Analysis

Efficacy analyses will be based on the ITT population. The null hypothesis for primary efficacy comparison is that the distribution of time to respiratory improvement (T2RI) between the two treatment groups is the same. The alternative hypothesis is that the distribution of T2RI between the two treatment groups is not the same. Rejecting the null hypothesis with shortened T2RI in PTC299 as compared with the placebo arm in the ITT population will be considered a successful demonstration of efficacy.

All statistical tests will be 2-sided at the significance level of 0.05. The corresponding p-values and 2-sided 95% CIs for intended point estimates will be reported.

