#### **4.10.2. Death**

The number and the percentage of deaths at Day 28 and Day 60, respectively, will be summarized by treatment groups.

All deaths will be presented in a by-subject listing.

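### The invasive-ventilation comparison has no rule for death, so a subject who dies without being counted as requiring ventilation scores the same as one who recovers

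*SAP*

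**What the plan says.** SAP 4.9.2.1 defines the numerator: "Number and the percentage of subjects requiring invasive ventilation during the study will be summarized by treatment groups". The test follows: "Cochran Mantel-Haenszel test will be used to compare the treatment difference". The strata for that test are not named. SAP 4.2.1 sets the denominator: "ITT population will include all randomized subjects. The ITT population will be used in all efficacy analyses". SAP 4.9 sets the level: "All statistical tests will be 2-sided at the significance level of 0.05". Protocol 4.3 excludes any subject who "Requires mechanical ventilation", so everyone starts as a non-event.

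For the primary endpoint the plan does have a death rule. In SAP 4.9.1, a subject who "died prior to Day 28" is censored at Day 28 and so is never counted as improved. The ventilation endpoint has no counterpart, either in SAP 4.9.2.1 or in Protocol 8.4.3. The three sensitivity analyses in SAP 4.9.1.1 concern the primary endpoint only.

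Death is a secondary endpoint in its own right ("Mortality at Day 28", SAP 2.2.2). SAP 4.10.2 provides its analysis: "The number and the percentage of deaths at Day 28 and Day 60" are summarized by arm, with a listing and no test. That section falls under SAP 4.10, which uses the safety population.

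**The concern.** Death ends a subject's chance of being ventilated. With every randomized subject in the denominator and no death rule, the endpoint cannot tell a subject who died unventilated from one who went home well. An arm can show less ventilation because fewer subjects deteriorated, or because more of those who deteriorated died first.

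The SAP attaches a p-value to this comparison and none to mortality. The outcome that death can distort is tested, and death itself is only counted. No planned table cross-classifies the two. The ventilation and death percentages cannot simply be added either, because some subjects who died will also have been ventilated.

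What is at stake is how one secondary result is read. The primary analysis is not affected.

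**Working it through.** **The plan's own figure.** None is given for this endpoint. The only stated power figure is for the primary endpoint, and it reproduces: Φ(√326 × ln 1.38 / 2 − 1.96) = Φ(0.948) = 82.8%, which agrees with the claim of more than 80%. It has no bearing here.

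**Inputs from the documents.** 190 subjects per arm (Protocol 4.1); numerator, denominator and test as set out above. **Not in the documents:** the proportion ventilated and the proportion dying unventilated. All counts below are assumptions.

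**Scoring.** Put each subject in one of three states: V, counted as requiring ventilation; D, died without being so counted; A, alive and never so counted. Per arm, V + D + A = 190. The endpoint is V/190, so D and A score alike. Moving one subject from V to D lowers the arm's rate by 1/190 = 0.53 points.

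**What drives the distortion.** Write Δ for PTC299 minus placebo. Then

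Δ(V) = Δ(V or D) − Δ(D).

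The written endpoint departs from the ventilation-or-death comparison by exactly the imbalance in unventilated deaths. If Δ(D) = 0, the two differences are identical.

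**Range of assumed counts (190 per arm).** The p-values come from an unstratified two-proportion z-test with pooled variance, as a stand-in for the CMH test.

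| Case | PTC299 V + D | Placebo V + D | As written, PTC299 vs placebo | p | Ventilation or death |
|---|---|---|---|---|---|
| Balanced | 20 + 4 | 20 + 4 | 10.5% vs 10.5% (0.0) | 1.00 | 12.6% vs 12.6% (0.0) |
| a | 20 + 6 | 24 + 2 | 10.5% vs 12.6% (−2.1) | 0.52 | 13.7% vs 13.7% (0.0) |
| b | 14 + 14 | 24 + 4 | 7.4% vs 12.6% (−5.3) | 0.087 | 14.7% vs 14.7% (0.0) |
| c | 14 + 16 | 28 + 2 | 7.4% vs 14.7% (−7.4) | 0.022 | 15.8% vs 15.8% (0.0) |
| d | 16 + 12 | 20 + 2 | 8.4% vs 10.5% (−2.1) | 0.48 | 14.7% vs 11.6% (+3.2) |
| e | 10 + 14 | 19 + 6 | 5.3% vs 10.0% (−4.7) | 0.08 | 12.6% vs 13.2% (−0.5) |

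Case c in full: difference = 14/190 − 28/190 = −0.0737; pooled p = 42/380 = 0.1105; SE = √(2 × 0.1105 × 0.8895 / 190) = 0.0322; z = −2.29; two-sided p = 0.022.

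In cases a to c the arms have the same total of ventilation or death, so the whole apparent difference of 2.1 to 7.4 points is an artefact. In case d the direction reverses. The largest distortion needs a large imbalance: 16 against 2 unventilated deaths in case c. Case c is also the only one with p below 0.05.

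**The case against.** The strongest reply is that the proportion requiring ventilation is a legitimate quantity, and that the plan reports death beside it. Mortality is a separate secondary endpoint, tabulated at Day 28 and Day 60 with a by-subject listing, and ventilated subjects are listed too. A death imbalance large enough to matter here would normally show in the mortality table, unless offset by deaths after ventilation. This stands as partial mitigation. It does not repair the comparison: the death table is untested, covers dosed subjects only, and leaves the reader to combine listings by hand.

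Second, the endpoint concerns subjects requiring ventilation, and the plan does not define requiring. A subject who needed ventilation but died without it, for example under a treatment limit, might be counted as an event. That reading would shrink the problem without removing it, since other deaths could still be non-events.

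Third, the weight is limited. Success rests on the primary endpoint (SAP 4.9), SAP 4.1 calls significance nominal, and Protocol 8.4.3 plans only frequency and percent for this endpoint. All of that is right, and it is why this is a small point.

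A reader might go further and infer that the plan treats death as a success, or that it ignores death altogether. The documents support neither. No section labels an unventilated death a success; the scoring follows from silence about death. Death is reported in its own right, and the primary analysis never counts a subject who died as improved.

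**Conclusion.** The gap is real and modest. As written, a subject who dies without being counted as requiring ventilation is a non-event in a tested comparison over all randomized subjects. If such deaths differ between arms, the comparison favours the arm with more of them, by the amount of the imbalance: 0.53 points per subject at 190 per arm.

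The documents do not show that a distortion will occur, or how large it would be. With balanced unventilated deaths the difference between arms is undistorted. The range of about 2 to 7 points rests on assumed counts with equal ventilation-or-death totals, and its upper end needs a marked death imbalance. It would also be smaller if requiring is read broadly. The trial's primary conclusion is not at risk. This is a cheap improvement to the plan.

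**What to change.** Keep the endpoint as stated. Add one sentence to SAP 4.9.2.1: the proportion of subjects with invasive ventilation or death by Day 28 will be summarized by arm in the ITT population and compared with the same CMH test. Present it as the row directly below the ventilation row.

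Two clarifications fit in the same edit: name the strata of the CMH test, and say how requiring is determined from the recorded data. The supplemental-oxygen or non-invasive-ventilation endpoint, also in SAP 4.9.2.1, has the same silence about death and could be treated the same way.

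The cost is a sentence and a table row. Ventilation and deaths are already collected. The downside is one more nominal secondary comparison, which should be labelled as such. The change should be made before database lock and unblinding so that it is not a post hoc choice.
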